8.4.4 Pharmacokinetic analysis

Levosimendan, OR-1855, OR-1896 and riluzole concentrations will be summarised using descriptive statistics. Metabolites OR-1855 and OR-1896 will be further summarised by subject acetylation status.

8.4.5 Population PK/PD modelling

A population pharmacokinetic/pharmacodynamic (PK/PD) model between OR-1896 and OR-1855 exposure and efficacy related endpoints will be explored. This will include building population PK model, and characterising the concentration effect relationship with PD endpoints.

8.4.6 Evaluation of pharmacogenomics

Acetylation status will be determined from all subjects participating in the study and the results will be source data. Acetylation status will be summarised by treatments groups. The effects of

DNO 090017ff823c9bac / 1.0 **Approved** 47 / 58

acetylation status on OR-1896 and OR-1855 pharmacokinetics and on SVC and HR will be evaluated using analysis of variance (ANOVA).

In the context of this study, genetic polymorphisms will be analysed in relation to significant variation or specific scientific questions in PK, PD or safety variables of levosimendan. These pharmacogenomic analyses apply only to those subjects who have signed a separate IC for PG. If such analysis is performed, the results will be reported in a separate report.

8.4.7 Evaluation of exploratory biomarkers

In the context of exploratory biomarker analyses, microRNA, proteins or biochemical metabolites may give supportive data related to the disease state of the patients and pharmacodynamics of levosimendan. If such analysis will be performed, the results will be reported in a separate report.

8.4.8 Safety analysis

An authorised person will code AEs, prior and concomitant medications using standard coding dictionaries.

8.4.8.1 Analysis of adverse events

AEs reported during the study will be classified by system organ classes and preferred terms using the Medical Dictionary for Regulatory Activities (MedDRA) coding system. The AEs will be displayed in a frequency table. The number and proportion (%) of subjects having each AE will be given, the severity of AEs (mild, moderate, severe) and causality to the study treatment will be evaluated. SAEs and other significant AEs will be evaluated case by case. AEs occurring before and after the start of study treatment will be reported separately.

8.4.8.2 Clinical safety analysis

Vital signs (supine and orthostatic HR, systolic and diastolic BP) as well as standard 12-lead ECG variables will be tabulated by treatment. Potential treatment effects will be analysed using the MMRM. The number of subjects with QTc interval prolongation will be classified and summarised. The details of the MMRM model and categorical analyses will be defined in the SAP. Abnormal ECG findings, special situations and physical examination findings will be summarised by treatment group using descriptive statistics.

8.4.8.3 Laboratory safety analysis

Safety laboratory results will be primarily evaluated using descriptive statistics and line plots only. Potential treatment effects may be analysed using the MMRM, if deemed necessary. The frequencies of normal and abnormal safety laboratory findings will be summarised based on the provided reference ranges of the respective laboratory, and the clinical significance of the findings will be evaluated.

DNO 090017ff823c9bac / 1.0 Approved 48 / 58

8.4.8.4 Analysis of prior and concomitant treatments

Prior and concomitant treatments will be coded using the anatomical therapeutic chemical (ATC) classification system. The number and percentage of subjects using concomitant treatments will be summarised by pharmacological subgroup and chemical substance.

8.4.8.5 Analysis of suicidality

Suicidality will be summarised by treatment group using descriptive statistics.

8.5 Interim analyses

Interim/futility analyses will be done when approximately 50% and 100% of the subjects have been treated for 12 weeks. Futility will be evaluated using SVC% response and time to respiratory event endpoint. Based on the estimation, approximately 35% and 75% of the respiratory events have cumulated at the time of planned analyses. Stopping criteria will be based on O'Brien-Fleming type of boundaries (O'Brien PC et al., 1979, Lan GKK et al., 1983). Exact alpha spending for futility analyses will be based on the actual amount of information used and are detailed in a DSMB charter. An independent DSMB will perform and evaluate the interim/futility analyses and make recommendations for the study conduct.

9. DATA QUALITY ASSURANCE

9.1 Training

An investigators' meeting will be arranged for the investigators and other relevant study centre personnel. This meeting will include a review of the protocol, CRF completion and study procedures as well as training on efficacy assessments like supine SVC and ALSFRS-R.

The investigators will ensure that appropriate training relevant to the study is given to the medical, nursing and other personnel involved in the study. The investigators will also ensure that any information relevant to the conduct of the study is forwarded to other relevant study centre personnel.

9.2 Case report forms

Electronic queries about missing, misleading, incomplete or illogical data will appear in the EDC system. An audit trail within the system will track all changes/corrections made. The investigator has to confirm the content of the eCRF with an electronic signature.

9.3 Monitoring, audits and inspections

The study monitor will visit the study centre regularly as agreed by the investigator and the sponsor. The study monitor will ensure that the study complies with good clinical practice (GCP) and applicable regulatory requirements and that the protocol is followed in all aspects, including the randomisation procedure, accurate recording of results, reporting of AEs, drug accountability and record keeping. Furthermore, it will be verified that the clinical facilities remain appropriate,

DNO 090017ff823c9bac / 1.0 Approved 49 / 58

and that the CRFs correspond with source data. Further details regarding monitoring are presented in the monitoring manual.

The study may be audited by independent representative(s) of the sponsor or inspected by the competent authorities (CAs). For these purposes, the study monitor, auditors and inspectors will be allowed direct access to hospital or patient records/source data of the study subjects, original laboratory data etc., as far as they are related to the study.

It is essential that the investigator and other relevant members of the study centre team are available during the monitoring visits, audits and inspections, and that they devote sufficient time to these processes.

9.4 Laboratories and other vendors

A central laboratory will be used for laboratory safety measurements, ECG analyses and spirometry.

Details regarding laboratory safety measurements, ECG analyses and spirometry are presented in the separate instructions. Quality certificates are required from all safety laboratories.

Bioanalytics will be performed using validated methods.

10. FURTHER REQUIREMENTS AND GENERAL INFORMATION

10.1 Investigators and study administrative structure

10.1.1 Investigators

Should the investigator transfer one of his/her responsibilities to other members of the study centre team, he/she must have this approved by the representative of the sponsor and documented.

In the event of changes in key study centre team members, the responsible investigator must ensure that the successor is fully informed and capable of following the procedures.

A curriculum vitae in English must be obtained from all investigators who sign the protocol, and from other relevant persons.

10.1.2 Data and safety monitoring board

An independent DSMB will be established for the study. The duty of the DSMB is to protect the ethical and safety interests of the study subjects and all others who may possibly be exposed to study treatments. The DSMB safety meetings will occur by approximately bimonthly frequency. The DSMB will also perform and evaluate formal futility/interim analyses and make recommendations for the study conduct.

Further details regarding the composition and responsibility of the DSMB are presented in a DSMB charter.

DNO 090017ff823c9bac / 1.0 Approved 50 / 58

10.2 Amendments to the study protocol

Any change or addition to the protocol can only be made in a written protocol amendment that must be approved by the sponsor, and when required by the EC/IRB or CA. Only in the event of a need to eliminate an immediate hazard(s) to study subjects, the investigator may implement a deviation from the protocol without prior approval.

Any change or addition to the approved study protocol may lead to suspension of the study or its results.

Any changes to the study protocol are subject to prior discussion with, and approval by, the sponsor and the study coordinating investigator. As a general rule, protocol amendments should be approved according to the same procedures as the study protocol.

Amendments are regarded as substantial, where they are likely to have a significant impact on the safety, physical or mental integrity of the study subjects, or the scientific value of the study. An approval of the responsible EC/IRB or CA shall be obtained before substantial amendments may be implemented, unless local regulations are different.

If an amendment contains only minor changes (typically administrative) not affecting the safety, physical or mental integrity of the study subjects, or the scientific value of the study, the EC/IRB or CA need not to be notified and in-house approval (including approval by the study coordinating investigator) is adequate.

10.3 Insurance

The sponsor will provide clinical trial liability insurance for study subjects in all participating countries according to local regulations.

10.4 Financial disclosure

The investigator will be required to disclose any financial arrangement whereby the value of the compensation for conducting the study could be influenced by the outcome of the study; any significant payments of other sorts from the sponsor, such as a grant to fund on-going research, compensation in the form of equipment, retainer for on-going consultation, or honoraria; any proprietary interest in oral levosimendan; any significant equity interest in the sponsor as defined in the US Code of Federal Regulations [21 CFR 54 2(b)].

In consideration of participation in the study, the sponsor will pay the investigator, or nominated payee the sums set out in the payment schedule attached to the Investigator Agreement.

10.5 Completion of the study

The end of the study is defined as the date of the last subject's last visit or last contact with the study site.

Study centres will be closed upon study completion. A study centre is considered closed when all required documents and study supplies have been collected and a study completion/termination visit has been performed.

DNO 090017ff823c9bac / 1.0 Approved 51/58

The sponsor reserves the right to prematurely terminate the study, or recruitment to the study, for valid scientific or administrative reasons. After decision to prematurely terminate the study, the investigator must contact all participating study subjects within 7 days, and invite them for an end-of-study visit.

10.6 Reports, publications and communication of results

Orion wishes to collaborate with the investigators to publish the results as timely as possible, without compromising accuracy or industrial property rights. The preparation, submission and authorship for publications containing the study results shall be in accordance with a process determined by mutual written agreement among the sponsor and participating investigators/institutions, and in accordance with international criteria for authorship; see International Committee of Medical Journal Editors recommendations, available at http://www.icmje.org.

Orion remains the exclusive owner of the study data defined by the protocol.

This study will be registered in one of the acceptable registries before the enrolment of the first subject.

10.7 Retention of records

The investigator agrees to keep the following documentation in the investigator's study file: study subject records, including a subject screening log, a subject identification list, all original signed IC forms, a copy of CRFs and records of drug dispensing.

The study files at the study centres will be stored in the respective archives for 15 years, after which the sponsor will be contacted and the possibility of future archiving will be mutually agreed upon.

11. ETHICS

11.1 Ethics committee

The study protocol, subject information sheet, IC form, and all other necessary documents will be submitted to an independent EC/IRB for review according to local regulations.

The investigator is responsible for obtaining a favourable opinion from the EC/IRB for the study, submitting any amendment(s), and communicating study-related safety issues as requested by the EC/IRB. The investigator should file all correspondence with the EC/IRB in the investigator's study file. Relevant copies of this correspondence should be forwarded to the sponsor.

11.2 Ethical conduct of the study

The study will be conducted in accordance with the Declaration of Helsinki guiding physicians in biomedical research involving human subjects.

The study shall not be initiated before favourable opinion from the EC/IRB and approval from the CA has been obtained for the protocol, including its appendices.

The study will be conducted in compliance with the protocol, GCP (ICH/135/95) and applicable regulatory requirements. A substantial amendment shall not be implemented until the protocol amendment has received favourable opinion from the EC and approval from the CA. Only in case of the need to eliminate an immediate hazard(s) to study subjects, the investigator may implement deviation from the protocol without prior favourable opinion from the EC and approval from the CA for the protocol amendment.

In case of serious breaches, the Medicines and Healthcare Products Regulatory Agency (MHRA) GCP Inspectorate must be notified according to MHRA Guidance for the notification of serious breaches of GCP or the study protocol (see http://www.mhra.gov.uk).

11.3 Subject information and informed consent

The investigator will ensure that each subject candidate is fully informed about the objectives and procedures of the study. The investigator will also explain any possible risks with participating in the study and answer all questions regarding the study. In the case that the subject is unable to sign the consent form due to muscular weakness, a witness may sign the form to indicate that the subject has given oral consent to participate in the study. In such cases, the investigator must also explain the study to the witness at the same time as they explain the study to the participant. After this, the subject will be given sufficient time to make a decision regarding participation in the study.

Subjects will be informed of their right to discontinue the study at any time without their medical care or legal rights being affected. Subjects will also be informed that representatives of the sponsor or CA may inspect relevant parts of their medical records and study data.

The investigator will obtain a signed and dated consent from each subject before any study related procedures are performed. A copy of each signed and dated IC will be given to the subject. The investigator should confirm the receipt of every IC by entering the date of the consent both on the subject's CRF and also on the subject screening log and identification list.

11.4 Subject data protection

Information collected during the course of the study will be stored in a database and used in the further development of oral levosimendan and thereafter for as long as the information is relevant to patient care. The use includes the transfer of data to CAs in the European Union, the USA or other countries for the purpose of obtaining and maintaining marketing authorisations. All information is handled confidentially and according to local laws and regulations.

The study subjects can be identified in the CRFs only by study subject number, birth year and sex.

The confidentiality of PG data will be protected according to local laws and regulations.

13.1 Revision history

Protocol and amended protocols	Date	Applies to	
Clinical study protocol	20 October 2017	Global	
Amendment 1 - Amended clinical study protocol	05 January 2018	Global	
Amendment 2 - Amended clinical study protocol	17 April 2018	Global	
Amendment 3 - Amended clinical study protocol	26 March 2020	Global	

Country specific amendments	Date	Applies to
Amendment 1	27 Mar 2018	Sweden
Amendment 1	06 Apr 2018	The United Kingdom
Amendment 1	16 Apr 2018	Belgium

13.2 Summary of changes

The changes incorporated in this amended protocol from the Amendment 2 – Amended clinical study protocol dated 17 April 2018 are described in the following. The modifications of the text are indicated by strikethrough (for deletions) and underline (for additions).

DNO 090017ff823c9bac / 1.0 **Approved** 56 / 58

The following changes were made due to COVID-19 nandemic:

Section	Previous text	New text	Rationale for the change
6.6 Changes implemented due to COVID-19 pandemic	-	Whole text is new, see the section 6.6.	New section describing changes due to COVID-19 pandemic added

In addition,

- the table of contents was updated to reflect the headings and pagination of the current document.
 the title page and header and footer sections were updated to reflect the version details of the current document.
- the approver information was updated.

1. GENERAL REMARKS

[figure not shown]
The purpose of this document is to describe the statistical methodology for this clinical study, including also plans of analysis datasets to be used and the plans how the results will be presented.

2. OVERALL STUDY DESIGN AND PLAN

This is a randomised, double-blind, placebo-controlled, parallel-group, multinational, multicentre phase III study. The subjects will be allocated to 2 parallel groups receiving either levosimendan 1-2 mg daily or placebo in 2:1 ratio. The study will be conducted globally. The estimated number of sites is approximately 100.

The total duration for double-blind comparison will be 48 weeks. The primary efficacy analysis will be based on data collected from the first 12 weeks of the study. Two futility/interim analyses will be conducted: the first when approximately 50%, and the second when all of the subjects have been treated for 12 weeks. An independent data and safety monitoring board (DSMB) will be established for this and for safety monitoring purposes.

There will be a screening visit, a baseline visit (V1) followed by visits at 2 weeks (V2), 4 weeks (V3), 8 weeks (V4), 12 weeks (V5), 24 weeks (V6), 36 weeks (V7) and 48 weeks (V8), and telephone contacts during weeks 18, 30 and 42. An end-of-study visit will take place 14-25 days after the last study treatment administration for each subject. Additional visits may take place after visit 3 and after later visits. The total study duration for each subject will be about 51-52 weeks, including the end-of-study visit. The study design is presented in [Figure 1](#).

¹ Dose will be increased if the 1 mg/day dosing was well tolerated

² Dose can be decreased back to 1 mg/day if required for any reason. In case the dose was decreased due to HR increase > 30 bpm, additional visit will take place after approx. 2 weeks

³ Any time during the week

Figure 1. Study design

3. STUDY OBJECTIVES

3.1 Primary objective

The primary objective of this study is to confirm that levosimendan can significantly improve respiratory function measured by supine slow vital capacity (SVC) in amyotrophic lateral sclerosis (ALS) patients.

3.2 Secondary objectives

The secondary objective is to confirm that levosimendan improves the functionality of subjects measured by Revised ALS Functional Rating Scale (ALSFRS-R), Clinical Global Impression (CGI), Borg Category Ratio 10 (CR10) scale on the intensity of dyspnoea, Epworth Sleepiness Scale (ESS) and Pittsburgh Sleep Quality Index (PSQI). The latter two are sleep scales assessing daytime somnolence and sleep quality, respectively. In addition, the long-term tolerability and safety of levosimendan in ALS patients will be evaluated, assessing up to 48 weeks of exposure.

3.2.1 Other objectives

For the purposes of potential later pharmacoeconomic analysis, the use of specific health care resources will be quantified on weekly basis, including:

- The number of days spent in hospital care.
- The number of additional visits to a hospital emergency unit.
- The average number of formal home care hours per day on the given week (paid/public services obtained) and the number of times such care was received during a usual night.
- The average number of informal home care hours per day on the given week (unpaid; by family, other relative, friend or volunteer) and the number of times such care was received during a usual night.
- The number of days spent in institutional care other than hospital (e.g. respite/hospice/nursing home/rehabilitative care).
- Receipt of new, non-medicinal assistive devices and other aids.

3.2.2 Exploratory objectives

The plasma concentrations of levosimendan and the metabolites OR-1855 and OR-1896 will be determined. In addition, a population pharmacokinetic/pharmacodynamic (PK/PD) model between OR-1855 and OR-1896 exposure and efficacy related endpoints and HR will be explored. Plasma concentrations of riluzole will also be determined. The effects of levosimendan, OR-1855 and OR-1896 on plasma trough concentrations of riluzole will be evaluated.

The acetylation status will be determined for all subjects to assess whether it affects the PD responses of levosimendan in patients with ALS.

4. STATISTICAL HYPOTHESES

A mixed model for repeated measures (MMRM) will be fitted for the change from baseline in supine slow vital capacity. The model will include data from all visit up to Week 12.

The difference between treatment groups at Week 12 is estimated from the MMRM with the use of contrasts, such that the quantity of interest is given by

$$\theta = \beta_{treatment} + \beta_{treatment \times week12}$$

The following null (H_0) and alternative (H_1) hypotheses will be used for testing the statistical significance of θ :

$$H_0: \theta = 0$$

$$H_1: \theta \neq 0$$

5. DETERMINATION OF SAMPLE SIZE

Sample size estimation is based primarily on supine SVC results from the study 3119001 LEVALS (Table 1). LEVALS had placebo-controlled data only up to 2 weeks, and therefore extrapolation of the results was needed. The placebo effect from phase II tirasemtiv trial BENEFIT-ALS (Shefner JM et al., 2016) was also evaluated.

Assuming a difference of at least 3.6% in change from baseline supine SVC between treatment groups and a common standard deviation of 10%, 164 evaluable subjects per group in a 1:1 allocation ratio have 90% power to detect a statistically significant difference in a two-sided, 5% α -level, two group T-test. Using a 2:1 allocation ratio, randomisation of 450 subjects to the study (approximately 300 levosimendan and 150 placebo treated subjects) allows for a total dropout rate of approximately 20%.

Table 1. Mean (SD) change from baseline SVC (supine) %-predicted in LEVALS

Treatment	2 weeks	12 weeks
Levosimendan 1 mg x 2	+2.4 (8.3)	-4.9
Levosimendan 1 mg x 1	+0.8 (8.6)	
Placebo	-3.6 (9.4)	-17.7 ¹
Placebo (BENEFIT-ALS)	-1.4	-8.5

¹ Extrapolated from the data

SD = standard deviation

Based on the dexpramipexole phase III study EMPOWER (Cudkowicz ME et al., 2013), a 12 point reduction in total ALSFRS-R score and a 15% mortality rate at 12 months can be assumed

in placebo treated patients. Assuming a 10 point decline in ALSFRS-R, with a standard deviation of 8 points, and a 20% relative improvement in survival, 450 patients provide approximately 80% simulated power to detect a statistically significant difference using a joint rank test. With 450 subjects and assuming a 48-week levosimendan event rate of 73% and hazard ratio of 0.70, time to respiratory event has approximately 70% power to detect a statistically significant difference using a log-rank test.

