8.2 Estimation of sample size

Sample size estimation is primarily based on the study 3119001 LEVALS SVC (supine) results (Table 6). The LEVALS study had placebo controlled data only up to 2 weeks and therefore extrapolation of the results is needed. The placebo effect from phase II tirasemtiv trial BENEFIT-ALS (Shefner JM et al., 2016) is also evaluated.

Assuming at least 3.6% difference between treatment arms and common standard deviation of 10%, 164 evaluable subjects have 90% power to detect a statistically significant difference at two-sided 5% level using 1:1 allocation ratio and two group T-test. Randomisation of 450 subjects to study using a 2:1 allocation ratio (approximately 300 levosimendan and 150 placebo treated subjects) allows approximately 20% drop out rate.

Based on dexpramipexole phase III study EMPOWER (Cudkowicz ME et al., 2013) 12 point reduction in total ALSFRS-R score and a 15% mortality rate at 12 months can be assumed in placebo treated patients. Assuming 10 point decline, with 8 point standard deviation, in ALSFRS-R and 20% relative improvement in survival 450 patients provide approximately 80% simulated power to detect statistically significant difference using joint rank test. With 450 subjects and assuming 48 week levosimendan event rate of 73% and hazard ratio of 0.70, time to respiratory event has approximately 70% power to detect statistically significant difference using log-rank test.

Table 6.	Mean ((SD)	change fi	rom base	line	SVC ((supine)

Treatment	2 weeks	12 weeks
Levosimendan 1 mg x 2	+2.4 (8.3)	-4.9
Levosimendan 1 mg x 1	+0.8 (8.6)	
Placebo	-3.6 (9.4)	-17.7 ¹
Placebo (BENEFIT-ALS)	-1.4	-8.5

¹ Extrapolated from the data

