6.2 Statistical issues

6.2.1 Randomization

Randomization will be conducted centrally using Medidata Rave RTSM. The subjects will be allocated to 2 parallel groups receiving either levosimendan 1-2 mg daily or placebo in 2:1 ratio.

The estimated number of sites is approximately 100 and randomization will not be stratified by centre. Randomization will be stratified by the following factors:

1. Bulbar onset
2. Edaravone use
3. North American region

The stratification variable used to adjust the statistical models will combine all three randomization factors into a single factor with $2^3 = 8$ distinct levels.

Due to data entry errors at randomization, levels of the stratification factors used for randomization may differ from final CRF data. Primary analyses will be conducted with the levels of stratification factors used for randomization (STRATAR in ADSL), while final CRF data will be used in a sensitivity analysis (STRATAV in ADSL; see 7.5.4).

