6.2.2 Significance level and confidence intervals

Two-sided tests with a significance level of 5% will be used throughout the analyses. Corresponding 95% confidence intervals will be calculated for model-based contrasts, comparing the active treatment to placebo, using model-based standard error estimates.

The study has interim analyses that allow early stopping for futility, but not for efficacy. Therefore, we do not make adjustments to the significance levels in the final analyses.

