Tipping point analyses will be considered for further evaluating sensitivity of the results with respect to missing data. In such an analysis, the distribution of missing data in the active treatment group would be shifted by varying amounts, until a point is found where the results of the analysis cross the threshold of statistical significance specified in section 6.2.2. The plausibility of a shift of the found size is then used to assess the robustness of results to unobserved differences due to missing data.

Subjects who discontinue study treatment but remain in the study can continue to contribute ALSFRS-R data, which will be included in the analyses where applicable. However, in time-to-

event analyses subjects will be censored from follow-up one day after study treatment discontinuation.

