7.5.2 Secondary efficacy variables

The following secondary efficacy endpoints will be tested in the hierarchy below in order to preserve the overall alpha level:

1. Combined assessment of function and survival (CAFS) through 48 weeks
2. Time to respiratory event
3. Clinical Global Impression (CGI) through 48 weeks
4. Supine Borg CR 10 scale at 12 weeks
5. Slope of change in the ALSFRS-R respiratory domain through 48 weeks

The endpoints and their methods of analysis are described in the following sections. Endpoints and analyses that are not listed in the testing hierarchy are included for supportive purposes only.

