7.5.2.2 Combined assessment of function and survival

Combined assessment of function and survival (CAFS) is a rank score based on the subject's survival time and change in ALSFRS-R score (Berry JD et al., 2013). A higher CAFS score for a subject indicates a better outcome relative to other subjects in the study.

To find the CAFS score, a sum score is calculated for each subject by comparing their status to all other subjects. In each individual comparison, the subject's score is incremented if they fared better than the other, and decremented if they fared worse. If their outcomes are equal, the score remains unchanged. This process produces an equivalent ordering to simply ranking the subjects based on their outcomes, and breaking ties with the given hierarchy of outcomes. The ordering between the subjects' outcomes is determined first by survival status: if both subjects died, then by survival time; and if both subjects survived, finally by the change from baseline ALSFRS-R score. Once these scores have been calculated for all subjects, they are ranked, from lowest (died first) to highest (best ALSFRS-R outcome among those who survived), yielding the final CAFS score used as the endpoint.

CAFS is analysed using the Wilcoxon-Mann-Whitney test to compare mean scores between the treatment groups at the Week 48 study visit. Statistical significance will be assessed based on the confidence interval derived for the Hodges-Lehmann estimator. In additional analyses, CAFS will also be assessed at the Week 12 and Week 24 study visits.

SAS code in the following fashion will be used to conduct the analysis:

```
proc npar1way data = ADEFF wilcoxon hl;
```

```
where ITTFL = "Y" and PARAMCD = "CAFS" and AVISIT = "Week 48";  
class TRTP;  
var AVAL;  
run;
```

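### The roughly 80% power stated for CAFS, the first secondary test, does not follow from its printed inputs, which give about 65% with complete data

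*SAP*

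**What the plan says.** SAP section 5 takes its placebo assumptions from an external phase III ALS trial of dexpramipexole: a 12-point fall in total ALSFRS-R and 15% mortality at 12 months. It continues: "Assuming a 10 point decline in ALSFRS-R, with a standard deviation of 8 points", and with "a 20% relative improvement in survival, 450 patients provide approximately 80% simulated power to detect a statistically significant difference using a joint rank test". Protocol 8.2 repeats the inputs and the result: "450 patients provide approximately 80% simulated power to detect statistically significant difference using joint rank test".

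The rest of the design is fixed elsewhere in the SAP:

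- Allocation (6.2.1): "receiving either levosimendan 1-2 mg daily or placebo in 2:1 ratio". Section 5 puts this at about 300 and 150 subjects.
- Sidedness (6.2.2): "Two-sided tests with a significance level of 5% will be used throughout the analyses".
- Ranking and test (7.5.2.2): deaths rank below survivors and are ordered by survival time. Survivors are ordered by ALSFRS-R change. The groups are compared at Week 48 with the Wilcoxon-Mann-Whitney test.
- Position (7.5.2): "The following secondary efficacy endpoints will be tested in the hierarchy below in order to preserve the overall alpha level". CAFS comes first of five.

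Neither document gives a death-time model, allocation, sidedness or missing-data rule for the simulation behind the CAFS figure.

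**The concern.** A 2-point difference against an SD of 8 is a standardised effect of 0.25. A fall in mortality from 15% to 12% adds little separation in the ranks. With 300 versus 150 subjects, 80% looks too high.

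The figure matters because of where CAFS stands. In a fixed sequence, a non-significant first test means that none of the other four secondary endpoints (time to respiratory event, CGI, supine Borg CR10, slope of the ALSFRS-R respiratory domain) can be claimed. A reader who relies on the stated power would put the risk of missing at that step at about one in five.

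**Working it through.** **Check of the approach on another figure in the same section.** For SVC (difference 3.6, SD 10, two-sided 5%), the normal approximation gives:

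- 164 per group: SE = 10 × √(2/164) = 1.104; power = Φ(3.6/1.104 − 1.96) = 90.3%.
- 240/120, which is 300/150 less 20%: SE = 10 × √(1/240 + 1/120) = 1.118; power = 89.6%.

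The SVC statement reproduces.

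**CAFS inputs.** Declines of 12 and 10 points, SD 8, placebo mortality 15%, 300/150, two-sided 5%. The 20% survival improvement cannot apply to the proportion surviving, because 0.85 × 1.2 = 1.02. Applied to mortality it gives 0.15 × 0.8 = 12%.

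**Probability that a levosimendan subject outranks a placebo subject.**

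- Both survive: 0.88 × 0.85 × Φ(2/(8√2)) = 0.748 × 0.5702 = 0.4265
- Only the levosimendan subject survives: 0.88 × 0.15 = 0.1320
- Both die, order taken as even: 0.5 × 0.12 × 0.15 = 0.0090
- Sum: 0.5675

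**Power.** The null SE of the Wilcoxon-Mann-Whitney probability is √(451/(12 × 300 × 150)) = 0.0289. Then z = 0.0675/0.0289 = 2.335, and power = Φ(2.335 − 1.960) = **64.6%**.

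A simulation with exponential death times, integer ALSFRS-R change and a tie-corrected test (20,000 runs) gave 65.3%, with a null rejection rate of 5.0%.

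**Other readings, by the same formula unless marked as simulated.**

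| Reading | Power |
|---|---|
| *Printed integers, 2:1, two-sided 5%* | |
| Hazard ratio 0.80 (mortality 1 − 0.85^0.8 = 12.2%) | 63.2% |
| Survival time × 1.2 (mortality 1 − 0.85^(1/1.2) = 12.7%) | 59.7% |
| Mortality rescaled from 12 months to 48 weeks (simulated) | 66% |
| Death and function correlated 0.3 to 0.9 (simulated) | 61–63% |
| *Departures from the printed inputs or the planned design* | |
| 10 points as placebo, improving to 8 (simulated) | 65% |
| 1:1 allocation (225/225) | 69.7% |
| One-sided 5%, 2:1 | 75.5% |
| One-sided 5%, 1:1 | 79.7% |
| 12 vs 9.6 points, 2:1 | 76.8% |
| 12 vs 9.6 points, 1:1 | 81.5% |
| Difference of 2.5 points, 2:1 | 79.5% |

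With the printed difference, SD and mortality, no two-sided 5% reading exceeds about 70%, even at 1:1. For scale, 80% at 2:1 on the printed inputs would take (1.960 + 0.842)²/(12 × (2/3) × (1/3) × 0.0675²) ≈ 646 subjects.

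**Two further figures, not needed for the conclusion.**

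- Under SAP 7.5.2.2, "Statistical significance will be assessed based on the confidence interval derived for the Hodges-Lehmann estimator". Applying this to one complete data set, and assuming the pooled SE is the interval width divided by 3.92, gives about 61% (8,000 runs).
- If 20% of subjects contributed nothing (240/120), power would be 55.1%. This is only a worst-case bound. The 20% allowance is stated for SVC. CAFS ranks deaths, uses all randomised subjects with multiple imputation, and under SAP 6.2.5 "Subjects who discontinue study treatment but remain in the study can continue to contribute ALSFRS-R data".

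**The case against.** The strongest reply is that the printed numbers may be rounded or incomplete.

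- **The 10-point decline is not assigned to an arm.** This is true. If it is a milder placebo value, no functional effect is printed and the power cannot be determined. But 12 versus 10 is the natural reading, and 10 improving by 20% to 8 gives the same 2-point difference and about 65%.
- **Rounding could cover the gap.** If 12 and 10 are both rounded, the true difference could lie between 1 and 3 points, and the formula then spans about 30% to 90%. A 9.6-point decline with SD 7.6 gives 80.1% at 2:1. This stands as a possible explanation, but it needs two values that the documents do not show. A reader given 12, 10 and 8 cannot get to 80%.
- **The consequence is limited.** The sample size rests primarily on SVC, and a secondary endpoint will be judged on its estimate and interval. This is correct, and it is why the point is one of reporting rather than design.
- **The 35% is not conditional on success in SVC.** Also correct. It is the chance that CAFS alone misses significance, and the conditional risk was not calculated.

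**Conclusion.** The concern holds. The printed inputs, under the plan's own allocation and sidedness, give about 65% power, roughly 15 points below the stated figure. The type II risk for the first secondary test is therefore about 35% where the text implies 20%.

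This assumes 12 points for placebo and 10 for levosimendan, a common SD of 8, mortality of 15% versus 12%, function independent of death, and complete data. Missing data would lower the figure. The error is in the stated power or in the stated inputs, and the documents do not show which. Type I error, sample size and the planned analysis are untouched. It should be corrected.

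**What to change.** Rerun the CAFS simulation and print its inputs in SAP section 5: decline in each group, SD, mortality in each group, death-time model, allocation, sidedness and missing-data handling. Then take one of two routes:

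- **If the inputs are those now printed**, replace the power with: *approximately 65% with complete data (12 vs 10 points, SD 8, mortality 15% vs 12%, 2:1, two-sided 5%); missing data would lower this*.
- **If other inputs were simulated**, print them with the power they give. A 9.6-point decline, for example, gives about 77% at 2:1.

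Record the correction in SAP 7.11 and carry it into Protocol 8.2 at the next amendment; it does not need an amendment of its own. The cost is one simulation rerun and one corrected sentence in each document. If the printed inputs stand, the stated power becomes less favourable. No patients are added, and the test, alpha and hierarchy do not change.
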